## 9. Secondary Statistical Analyses

### 9.1. Secondary Efficacy Analyses

Secondary efficacy analyses will be conducted in FAS and PPS.

The secondary efficacy endpoints include changes from baseline at each visit (except Week 24) of HbA1c, and changes from baseline at each visit of FPG, 0.5h PPG, 2h PPG, Fasting C-Peptide, 0.5-hour postprandial C-Peptide, 2-hour postprandial C-Peptide, Fasting Insulin, 0.5-hour postprandial Insulin, 2-hour postprandial Insulin. The same analysis method for the primary efficacy endpoint is used, i.e. MMRM.

HbA1c response rate and composite HbA1c response rate will be calculated on basis of data imputed using LOCF method. Odds ratio (OR) and its 95% CI between two treatment groups will be estimated using logistic regression method.

Other secondary endpoints, such as HOMA- $\beta$ , HOMA-IR, HOMA2- $\beta$ , HOMA2-IR, I0/G0,  $\Delta$  I30/  $\Delta$  G30,  $\Delta$  C30/  $\Delta$  G30,  $\Delta$  I120/  $\Delta$  G120 and change from baseline in DI will be analyzed and compared using covariance analysis model for each treatment group. Calculation will be based on data imputed by LOCF.

The value and change from baseline of HbA1c, fasting plasma glucose and 2-hour postprandial plasma glucose from the end of double-blind treatment period (Week 24) to the end of study (Week 52) will be summarized with descriptive statistics by group. One of the groups consists of subjects who were randomized into HMS5552 treatment group. Another group consists of subjects who were randomized into placebo group and then switch to HMMS5552 treatment in open-label treatment period. Data at the end of double-blind treatment period (Week 24) will be set as baseline to summarize the value and change from baseline at each visit in open-label treatment period.

### **9.1.1. Change from Baseline in HbA1c at Each Visit (Except Week 24)**

MMRM will be used, where the model is the same as primary endpoint analysis model. The model includes the factors of treatment group, visit, interaction of visit with treatment group, pooled site and baseline HbA1c. The point estimate and 95% CI of mean difference between treatment groups (HMS5552 75mg BID vs. Placebo BID) will be calculated.

### **9.1.2 Hba1c Response Rate (proportion of subjects with HbA1c< 7%)**

HbA1c Response Rate and composite HbA1c response rate will be calculated on basis of data imputed using LOCF method. The percentage pf subjects that with HbA1c < 7% at the end of double-blind treatment period (Week 24) will be summarized on basis of data imputed using LOCF method. Odds ratio (OR) and its 95% CI between two treatment groups will be estimated using logistic regression method. The model includes the factors of treatment group, pooled site, interaction of pooled site with treatment group and baseline HbA1c. If the interaction is not significant (2-sided alpha 0.1), then remove the interaction of pooled site with treatment group from model.

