### **9.3.6 Sensitivity Analysis**

Sensitivity analysis is applicable to the primary efficacy endpoint.

The LOCF approach is performed to impute missing primary efficacy endpoint. For subjects with early withdrawal, the last available post-treatment measurement is carried forward. The analysis of covariance (ANCOVA) model is used for analyzing the imputed data. The ANCOVA model includes baseline HbA1c value, disease duration, sites and groups as covariate, with or without the interactions between center and group. The adjusted least-squares mean difference between HMS5553 and placebo, and its 95% CI are estimated by ANCOVA. If p value of the between-group comparison is smaller than 0.05, it is considered that the between-group difference is statistically significant. If the upper limit of the 95% CI is smaller than 0, it is considered that HMS5552 is superior to placebo in treatment effect.

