## 2.4. Sample Size Determination

This study plans to recruit 450 subjects. The number of subjects may be increased by 20% if drop-out is considered. The total number of subjects will be no more than 564. Subjects are randomized at a ratio of 2:1 to the experimental group (HMS5552) or the control group (placebo), it is estimated that no more than 376 subjects in the experimental group and 188 subjects in the control group will be included.

Based on the planned sample size and the treatment assignment ratio (450 subjects, HMS5552 experimental group: control group = 2:1), a power of 91.4% would be provided to detect a difference of at least 0.4% in the change of HbA1c from baseline at week 24 between experimental group and control group, assuming there is no difference between the two groups with the standard deviation of 1.2% and the significance level of 0.05 (2-sided).

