### 5.1. Multicenter Study

HMM0301 is a multicenter study. Subjects from 40 centers will be enrolled

---

competitively.

Number of subjects in each site will be evaluated before unblinding. If the number of subjects meeting FAS criteria within the site is smaller than 10, it will be pooled with other sites in city to province order until the number of subjects in pooled sites is more than 10. If the number of subjects within the pooled site is still smaller than 10, then sites will be further pooled by geographic regions that defined as below:

- Beijing, Tianjin
- Three Northeast Provinces, Inner Mongolia
- Shandong, Hebei, Anhui, Henan
- Shanghai, Zhejiang, Jiangsu
- Hubei, Hunan, Jiangxi
- Yunnan, Sichuan, Guizhou, Chongqing
- Shaanxi, Shanxi
- Guangdong, Guangxi, Hainan
- Qinghai, Ningxia

Unless otherwise specified, efficacy analysis results will be summarized by pooled sites on basis of FAS and PPS population. Listing will be provided by the actual sites.

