### 8.1.1. Sensitivity Analyses of Primary Efficacy endpoint

1. The same analysis for the primary endpoint will be performed in PPS as in FAS.
2. Primary efficacy analysis based on LOCF imputation.

Change from baseline in HbA1c when treatment completed (Week 24) will be described for each group. ANCOVA will be used to compare the change from baseline (LOCF) between treatment groups. The model includes treatment group, pooled site, interaction of pooled site with treatment group and baseline HbA1c. If the interaction is not significant (2-sided alpha 0.1), then remove the interaction of pooled site with treatment group from model. A superiority test between treatment group and placebo group will be performed. Based on covariance analysis model, difference of adjusted mean between treatment group and placebo group, as well as its 95% CI, will be estimated.

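### The p<0.10 keep/drop rule for site-by-treatment can leave the responder odds ratio undefined; the main-effects model should be the only inferential one

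*Supplement*

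**What the plan says.** For the HbA1c <7% responder endpoint, SAP 9.1.2 promises an odds ratio with 95% CI from logistic regression. It specifies: "The model includes the factors of treatment group, pooled site, interaction of pooled site with treatment group and baseline HbA1c". It then applies a pre-test, worded the same way in SAP 8.1.1 for the LOCF ANCOVA of the primary endpoint: "If the interaction is not significant (2-sided alpha 0.1), then remove the interaction of pooled site with treatment group from model". The rule recurs in SAP 9.1.3 (<6.5% responders), 9.2 (HOMA and ratio indices), 9.2.7 (composite response) and 9.3.5 (weight). Protocol v1.1 section 9.3.6 had allowed the ANCOVA "with or without the interactions between center and group".

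On layout, SAP 5.1 states: "Subjects from 40 centers will be enrolled". Sites with fewer than 10 FAS subjects are pooled by city, then province, then into nine regions. Under SAP 5.2 randomisation is stratified only by baseline HbA1c (8.5% cut), not by site.

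The primary MMRM in SAP 8.1 has no site-by-treatment term.

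**The concern.** A pooled site just over the floor of 10 has three or four placebo subjects. If none of them responds, or all do, the interaction parameter for that site has no finite maximum likelihood estimate. The keep/drop decision is then taken from a model that cannot be fitted properly.

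The SAP does not say:

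- which test decides, although a two-sided alpha does not identify a test for a term with many degrees of freedom;
- how one odds ratio or one ANCOVA difference is formed if the term stays, that is, with what site weights or reference site;
- what happens on separation or when a site has no subject in one arm. The MMRM has a named fallback for non-convergence; the sparser logistic models have none.

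At stake are a named secondary endpoint (<7% responders), one of the two sensitivity analyses of the primary endpoint, and several exploratory and weight analyses. In each, the data would choose which treatment effect is reported.

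**Working it through.** **Inputs from the documents.** SAP 2.4: 450 subjects at 2:1 (300 and 150), difference 0.4, SD 1.2, two-sided alpha 0.05. SAP 5.1: 40 centres, pooling floor 10, nine regions at the last step. SAP 5.2: no site stratification.

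**Assumptions, not in the documents.** Placebo/active response of 8/20%, 15/35%, 20/45% or 30/50%; 9 to 40 pooled sites of at least 10 subjects; no true interaction unless stated.

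**The plan's own figure.** SE = 1.2 × √(1/150 + 1/300) = 0.12, and 0.4/0.12 = 3.33. Normal-approximation power is Φ(3.33 − 1.96) = 91.5%; the noncentral t with 448 df gives 91.4%, as stated. The calculation is for one common difference and allows for no site-by-treatment term.

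**Step 1: cell sizes.** 450/40 = 11.25 per site, or 11.25/3 = 3.75 on placebo. At nine pooled sites: 50 and 16.7.

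**Step 2: cells at 0% or 100%.** For a site of n subjects and placebo response p, the chance of no placebo responder is (1 − p/3)^n. With equal sites:

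- n = 11.25, p = 0.15: 0.95^11.25 = 0.56, so about 0.56 × 40 = 22 of 40 sites.
- n = 50, p = 0.08: 0.26, so 1 − 0.74^9 = 93% for at least one of nine sites.
- n = 50, p = 0.30: 0.0052, so 1 − 0.9948^9 = 4.5%.

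Simulation with uneven site sizes, all cells counted (ranges over the assumed response rates):

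| Pooled sites | At least one 0%/100% cell | Mean sites affected | Some site lacks an arm |
|---|---|---|---|
| 9 | 48–99% | 0.6–3.3 | about 1% |
| 15 | 88–100% | 1.8–7.7 | about 3% |
| 20 | 98–100% | 3.3–11.9 | about 6% |
| 30 | 100% | 7.8–21.5 | about 17% |
| 40 | 100% | 14.3–31.8 | about 37% |

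Other assumed site sizes lower the bottom of these ranges, to about 90% at 20 sites and about 6% at nine.

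**Step 3: the logistic pre-test at 0.10, no true interaction.** Baseline HbA1c was left out for simplicity.

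| Pooled sites | LR test keeps the term | Separated among kept fits |
|---|---|---|
| 9 | 13–14% | 73–100% |
| 20 | 10–24% | 99.6–100% |
| 30 | 7–32% | 100% |
| 40 | 3.5–45% | 100% |

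A repeat simulation over 9 to 40 sites gave 6–43%. In a further simulation (9 to 30 sites, divergent logits capped), a joint Wald test kept the term in 0–5% of runs, and in 0–0.3% at 20 or more sites, where LR kept it in 8–30% over the same settings. The nominal rate is 10%.

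**Step 4: ANCOVA, no true interaction.** The F pre-test keeps the term in about 10% of runs. The estimate, taken as the equal-weight LS-mean difference, then moves by a mean of 0.04–0.12 HbA1c points. Its SE goes from 0.121 to 0.157 at 10 sites, a variance ratio of (0.157/0.121)² = 1.68. At 40 sites it goes from 0.126 to about 0.129, a ratio of 1.05. Across layouts the variance penalty ran from about +3% to +77%.

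A non-estimable result needs the term kept and an empty cell. P(no placebo subject) is (2/3)^11 = 1.2% for a site of 11, and 1 − (1 − 0.012)^40 is about 37–38% over 40 sites. Multiplying, 0.10 × 0.37 = 3.7%. Simulated: 0.2–4%. With an assumed between-site SD of the effect of 0.4, the term is kept in 40–59% of runs and is non-estimable in 1–15%. Type I error stays at 0.045–0.057.

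**Step 5: main-effects model.** ANCOVA power at a 0.4 difference is 88–91%, against 84–89% under the rule with non-estimable runs counted as failures. The effect is estimable in every run. In the logistic model, a pooled site with all or no responders then affects only its own site term, and one common odds ratio remains.

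**The case against.** The strongest reply is that nothing confirmatory depends on the rule. The primary MMRM, its repeat in the PPS, and the MMRMs for FPG, PPG and HbA1c by visit contain no site-by-treatment term. Responder percentages are summarised whatever the model does, so only the odds ratio is exposed, and only if the term is kept. Forty is the count before pooling; with competitive enrolment, 40 surviving pooled sites would need an almost even spread. Under a Wald test the term nearly always goes, leaving the main-effects odds ratio.

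All of this stands, and it limits the weight of the point. It does not remove it. The SAP does not choose the Wald test, and a Wald test that drops the term because separation has inflated its standard errors says nothing about heterogeneity. The separated model has to be fitted before the rule can be applied at all.

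A reader might also infer that the protocol's wording on the ANCOVA interaction is a separate contradiction. It is not: protocol 9.3 leaves analysis detail to the SAP, and SAP 8.1.1 settles it.

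**Conclusion.** The point holds for the secondary responder endpoint, the LOCF sensitivity analysis, and the exploratory and weight analyses. Separated cells in the starting logistic model are very likely: about 90–100% at 20 or more pooled sites, and anywhere from about 6% to 98% at nine. With no true interaction, retention runs from almost never (Wald) to roughly 6–43% (LR). If the term is kept, the promised single odds ratio does not exist, and the ANCOVA contrast becomes an equal-weight site average with a precision loss that depends on site sizes. These figures rest on assumed response rates and site sizes.

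Three stronger readings are not supported:

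- That the primary result is at risk: its model has no such term.
- That false positives rise: ANCOVA type I error was 0.045–0.057.
- That the chance of an empty cell, up to about 37%, is the chance of a non-estimable effect: the term must also be kept, which brings it to about 0.2–4% with no true interaction.

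This should be corrected, but it does not threaten the trial's main conclusion.

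**What to change.** In SAP 8.1.1, 9.1.2, 9.1.3, 9.2, 9.2.7 and 9.3.5, delete the 0.10 keep/drop rule. State that the model with treatment, pooled site and the relevant baseline is the only inferential model, matching the covariate structure of the primary MMRM. Show site-by-treatment heterogeneity descriptively, as a table or forest plot by pooled site.

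The cost is SAP wording and slightly less programming. The small downside is that no formal interaction model is used for inference. Replacing pooled site by region, Firth penalisation, an added risk difference and a protocol amendment are not needed to mend this.

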### **9.1.3 Hba1c Response Rate (proportion of subjects with HbA1c< 6.5%)**

HbA1c Response Rate and composite HbA1c response rate will be calculated on basis of data imputed using LOCF method. The percentage pf subjects that with HbA1c < 6.5% at the end of double-blind treatment period (Week 24) will be summarized on basis of data imputed using LOCF method. Odds ratio (OR) and its 95% CI between two treatment groups will be estimated using logistic regression method. The model includes the factors of treatment group, pooled site, interaction of pooled site with treatment group and baseline HbA1c. If the interaction is not significant (2-sided alpha 0.1), then remove the interaction of pooled site with treatment group from model.

#### 9.1.4 Change from Baseline in Fasting Plasma Glucose (FPG)

MMRM will be used, where the model is the same as primary endpoint analysis model. The model includes the factors of treatment group, visit, interaction of visit with treatment group, pooled site and baseline fasting plasma glucose. The point estimate and 95% CI of mean difference between treatment groups (HMS5552 75mg BID vs. Placebo BID) will be calculated.

#### 9.1.5 Change in Baseline in Postprandial Plasma Glucose (PPG)

MMRM will be used, where the model is the same as primary endpoint analysis model. The model includes the factors of treatment group, visit, interaction of visit with treatment group, pooled site and baseline 2-hour postprandial plasma glucose. The point estimate and 95% CI of mean difference between treatment groups (HMS5552 75mg BID vs. Placebo BID) will be calculated.

MMRM will be used in the analysis of 0.5-hour postprandial plasma glucose, where the model is the same as the analysis of 2-hour postprandial plasma glucose. The model includes the factors of treatment group, visit, interaction of visit with treatment group, pooled site and baseline 2-hour postprandial plasma glucose.

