### **2.2.2.2. Secondary Endpoints**

To compare the treatment group (HMS5552 tablets 75 mg BID, oral) with placebo group after each of 24-week double-blind treatment and additional 28-week open-label treatment (Week 52):

- Change of 0.5-hour postprandial plasma glucose (0.5h PPG) from baseline
- Change of 2-hour postprandial plasma glucose (2h PPG) from baseline
- Change of FPG from baseline
- HbA1c response rate: the proportion of subjects whose HbA1c < 7.0%
- Change of HbA1c from baseline at each visit, except Week 24

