### **9.2.2. 0.5-Hour Postprandial C-Peptide**

MMRM will be used, where the model is the same as primary endpoint analysis model. The model includes the factors of treatment group, visit, interaction of visit with treatment group, pooled site and baseline 0.5-hour postprandial C-Peptide. The point estimate and 95% CI of mean difference between treatment groups (HMS5552 75mg BID vs. Placebo BID) will be calculated.

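### SAP 9.1.5 adjusts the 0.5-hour postprandial glucose model for the 2-hour baseline instead of its own, which costs some precision on one SAP-level secondary endpoint

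*Supplement*

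**What the plan says.** SAP 2.2.2.2 lists "Change of 0.5-hour postprandial plasma glucose (0.5h PPG) from baseline" among the secondary endpoints. SAP 9.1 repeats this, placing "changes from baseline at each visit of FPG, 0.5h PPG, 2h PPG" among the secondary endpoints to be analysed by MMRM.

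SAP 9.1.5 has two paragraphs. The first gives the model for 2-hour PPG, with the 2-hour baseline as covariate, which is correct. The second deals with 0.5-hour PPG. It opens with "MMRM will be used in the analysis of 0.5-hour postprandial plasma glucose, where the model is the same as the analysis of 2-hour postprandial", so it refers back to the first paragraph, and then writes the factors out again, ending with "interaction of visit with treatment group, pooled site and baseline 2-hour postprandial plasma glucose". Baseline 0.5-hour PPG does not appear in that model, and no reason is given.

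The sibling sections do it differently. The FPG model (SAP 9.1.4) has "pooled site and baseline fasting plasma glucose". The 0.5-hour C-peptide model (SAP 9.2.2), which uses the same 30-minute draw, has "pooled site and baseline 0.5-hour postprandial C-Peptide".

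**The concern.** When the response is a change from baseline, the endpoint's own baseline is normally the covariate that matters most. Subjects with a high 0.5-hour value at baseline tend to fall and those with a low value tend to rise. Adjusting for the 0.5-hour baseline removes this regression to the mean from the comparison. Adjusting for the 2-hour baseline removes it only as far as the two baselines move together.

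Two things are at stake for this endpoint: a confidence interval wider than it need be, and a treatment difference that still carries part of any chance imbalance in baseline 0.5-hour PPG. Under SAP 2.3.2, note 12, the 30-minute sample is taken only in subjects enrolled after protocol v1.1 took effect. The loss therefore falls on a sample that may already be reduced. The documents do not say by how many.

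**Working it through.** **Is the wording isolated?** The covariates that the SAP spells out are:

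| Endpoint | SAP section | Baseline covariate |
|---|---|---|
| HbA1c | 8.1, 9.1.1 | own |
| FPG | 9.1.4 | own |
| 2-hour PPG | 9.1.5, first paragraph | own |
| **0.5-hour PPG** | **9.1.5, second paragraph** | **2-hour PPG** |
| Fasting, 0.5-hour, 2-hour C-peptide | 9.2.1 to 9.2.3 | own |
| Fasting, 0.5-hour, 2-hour insulin | 9.2.4 to 9.2.6 | own |
| HOMA and the other beta-cell indices (ANCOVA) | 9.2 | own |
| Weight (ANCOVA) | 9.3.5 | own |

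**Could missing baselines explain it?** No. SAP 6.3 sets the change to missing when the baseline is missing. Every subject with a 0.5-hour change therefore has a 0.5-hour baseline, and the own-baseline model loses nobody.

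**Plan's own figure.** The only stated design figure is 91.4% power for HbA1c (300:150, difference 0.4, SD 1.2, two-sided 0.05). It reproduces: 0.915 by the normal approximation and 0.914 by the noncentral t with 448 df. It does not bear on this point, and the plan states no figure for 0.5-hour PPG.

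**Size of the precision loss.** All of these inputs are assumptions:
- rho: correlation of 0.5-hour PPG at baseline with 0.5-hour PPG at follow-up.
- r: correlation of baseline 0.5-hour with baseline 2-hour PPG.
- s: correlation of baseline 2-hour PPG with follow-up 0.5-hour PPG. It is set to r × rho, meaning that the 2-hour baseline relates to follow-up only through the 0.5-hour baseline.
- Equal variances and a single visit.

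Residual variance of the change, in units of the common variance:
- own baseline: 2(1 − rho) − (1 − rho)² = 1 − rho²
- 2-hour baseline: 2(1 − rho) − (s − r)² = 2(1 − rho) − r²(1 − rho)²
- ratio: [2 − r²(1 − rho)] / (1 + rho), which exceeds 1 for every r below 1.

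| rho | r | Variance ratio | CI width ratio (square root) |
|---|---|---|---|
| 0.5 | 0.6 | (2 − 0.18)/1.5 = 1.21 | 1.10 |
| 0.5 | 0.8 | (2 − 0.32)/1.5 = 1.12 | 1.06 |
| 0.7 | 0.6 | (2 − 0.108)/1.7 = 1.11 | 1.05 |
| 0.7 | 0.8 | (2 − 0.192)/1.7 = 1.06 | 1.03 |

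Over rho 0.3 to 0.8 and r 0.3 to 0.9, the ratio runs from 1.02 (0.8, 0.9) to 1.49 (0.3, 0.3), which makes the CI 1% to 22% wider. A simulation with 4,000 replicates at 300:150 gave 1.15 against the formula's 1.17 at (0.5, 0.7), and 1.41 against 1.40 at (0.3, 0.5).

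**Chance imbalance.** Suppose the arms differ by d in baseline 0.5-hour PPG.
- If they are balanced on 2-hour PPG, the specified model leaves an error of −(1 − rho)d, or −0.5d at rho 0.5.
- If the 2-hour baseline shifts in step, by r × d, the error shrinks to −(1 − rho)(1 − r²)d. At rho 0.5 and r 0.7 this is −0.5 × 0.51 × d, about −0.26d.
- Own-baseline adjustment removes it in both cases.

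**The case against.** The strongest reply is that this is a one-phrase carry-over from the paragraph above, that the intended covariate is plain from the sibling sections, and that little hangs on it. Most of that stands.

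- **No bias on average.** A reader might infer that the estimate is biased. It is not: allocation is random, so both models estimate the same difference, and the specified model's interval remains valid, though probably wider. The imbalance error belongs to one realized sample and is not systematic. Because the two baselines are presumably correlated, the 2-hour covariate absorbs part of it.
- **Reach.** A reader might also infer that the trial's conclusion is at risk. It is not. The single powered test is HbA1c at Week 24. 0.5-hour PPG is not among the protocol v1.1 endpoints, nor in the SAP's own secondary objectives (SAP 2.2.1.2), and no claim is tied to it.
- **Size.** Every correlation is assumed, and the loss could be as small as about 2% in variance. The formula covers one visit, whereas the MMRM covers the Week 12 and Week 24 meal tests. The specified model would match or beat the own-baseline model only if |s − r| were at least 1 − rho. At rho 0.5 and r 0.7 that would need s at or below 0.2, against 0.35 under the assumption used here, which is an unlikely pattern.
- **Analysis set.** No further definition is needed. SAP 2.3.2 note 12, 6.3 and 9.1 together already settle who contributes.

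What does not stand is that the intention is safe to leave implicit. The paragraph does more than refer back to the 2-hour model: it lists the factors and names the 2-hour baseline. A programmer who follows it literally fits that model, and one who corrects it silently departs from the SAP.

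**Conclusion.** The covariate is wrong as written and no other section corrects it. The consequence is lost precision and incomplete adjustment for chance baseline imbalance, with no bias on average. At rho 0.5 to 0.7 and r 0.6 to 0.8 the single-visit variance is about 6% to 21% larger and the CI about 3% to 10% wider. Over the wider ranges the variance increase is about 2% to 49%. These figures rest on assumed correlations, equal variances and the indirect-relation assumption for the 2-hour baseline. Only this one SAP-level secondary endpoint is affected. Severity is minor to moderate.

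**What to change.** In the second paragraph of SAP 9.1.5, change the covariate to baseline 0.5-hour postprandial plasma glucose. Also reword the cross-reference so that it says the model has the same form as the 2-hour model, with the endpoint's own baseline. The cost is one sentence, with no new data and no subjects lost. Make the change before unblinding, in line with protocol 9.3, which requires the SAP to be final before database lock and unblinding. Made later, the same correction would be a departure chosen after the data could be seen.
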